6.1.2 Dosing Instructions

Participants will receive doses of AZD1222 or placebo on Day 1 and Day 29.

It is recommended that the study interventions be administered as an IM injection into the

deltoid of the non-dominant arm. If IM injection in the deltoid of the non-dominant arm is not possible (local injury, tattoo, other) then IM injection in the deltoid of the dominant arm may be used.

The injection site should be wiped with alcohol cotton and covered with a dressing. All participants will be observed for 30 minutes after vaccination at the study site. After the observation at the site, the study staff will attach a hermetic transparent dressing to the injection site. The application of the dressing will continue until the next visit. If the dressing comes off before the next visit, the participant should be instructed to put on the spare dressing. In addition, the peeled dressing should be properly stored in a sealed waste bag distributed beforehand. The participants will be instructed to bring it to the site at the next visit, and the study staff should collect it at the next visit. The staff will dispose of it properly.

Allergic reactions to vaccines are possible. Therefore, appropriate drugs and medical equipment to treat acute anaphylactic reactions must be immediately available, and study personnel must be trained to recognise and treat anaphylaxis.

6.2 Preparation/Handling/Storage/Accountability

- 1) The investigator or designee must confirm appropriate temperature conditions have been maintained during transit for all study intervention received and any discrepancies are reported and resolved before use of the study intervention.
- 2) Only participants enrolled in the study may receive study intervention and only authorised site staff may supply or administer study intervention. All study intervention must be stored in a secure, environmentally controlled, and monitored (manual or automated) area in accordance with the labelled storage conditions with access limited to the investigator and authorised site staff.
- 3) The investigator, institution, or the head of the medical institution (where applicable) is responsible for study intervention accountability, reconciliation, and record maintenance (ie, receipt, reconciliation, and final disposition records).
- 4) Further guidance and information for the final disposition of unused study interventions are provided in the Pharmacy manual or specified handling instructions.

6.2.1 Dose Preparation and Administration

6.2.1.1 AZD1222

Doses of AZD1222 must be prepared by the unblinded pharmacist (or designee in accordance with local and institutional regulations) using aseptic technique. Each dose is prepared by withdrawing 0.5 mL from a vial of AZD1222 in a sterile 1 mL or equivalent syringe.

AZD1222 does not contain preservatives, each vial must be assigned a beyond-use-date of 4 hours from first needle puncture of the AZD1222 vial, after which any unused portion must

be discarded. Once an AZD1222 dose is drawn into a syringe for administration, the dose must be administered according to the beyond-use-date of the vial. If AZD1222 dose administration is not completed within the 4 hour beyond-use-date, a new dose must be prepared from a new vial.

Each vial of AZD1222 has a label-claim volume of 5 mL and can provide up to ten 0.5 mL doses.

6.2.1.2 Placebo

Doses of placebo must be prepared by the unblinded pharmacist (or designee in accordance with local and institutional regulations) using aseptic technique. Each placebo dose is prepared by withdrawing 0.5 mL from a 0.9% (w/v) saline vial or intravenous (IV) bag in a sterile 1 mL or equivalent syringe. If 0.9% (w/v) saline is extracted from IV bags, the manufacturers recommendation for maximum number of needle punctures of the IV bag port must not be exceeded.

Saline (0.9% [w/v]) does not contain preservatives, each IV bag or vial must be assigned a beyond use date of 4 hours from first needle puncture, after which any unused portion must be discarded. Once a placebo dose is drawn into a syringe for administration, the dose must be administered according to the beyond-use-date of the vial. If placebo dose administration is not completed within the 4-hour beyond-use-date, a new dose must be prepared from a new vial or IV bag.

6.3 Measures to Minimise Bias: Randomisation and Blinding

6.3.1 Randomisation

All participants will be centrally assigned to randomised study intervention using an Interactive Response Technology (IRT). Before the study is initiated, user guides, the log in information, and directions for the IRT will be provided to each site.

The randomisation will be done separately within each Cohort. In Cohort D, participants will be stratified at randomisation by age group within cohort, but in Cohort C stratification will not be done.

Where a participant does not meet all the eligibility criteria but is randomised in error, or incorrectly received study intervention, the investigator should inform the sponsor's physician immediately, and a discussion should occur between the sponsor's physician and the investigator regarding whether to continue or discontinue the participant.

6.3.2 Blinding

Neither the participant nor any of the investigators or Sponsor staff who are involved in the treatment or clinical evaluation and monitoring of the participants will be aware of the study

intervention received until completion of clinical data lock for primary analysis. Only participants will be blinded from their investigational product assignment after clinical data lock for primary analysis. The study will become open label in order to inform participants of their investigational product assignment when a licensed vaccine for COVID-19 becomes available in Japan for the general population. Since AZD1222 and placebo are visually distinct prior to dose preparation (due to differences in container closure), investigational medicinal product will be handled by an unblinded pharmacist (or designee in accordance with local and institutional regulations) at the study site. Once drawn into syringes for administration, AZD1222 and placebo are not visually distinct from each other.

The IRT will provide to the investigator(s) or pharmacists a dose tracking number to be allocated to the participant at the vaccination visit. Routines for this will be described in the IRT user manual that will be provided to each site.

The randomisation code should not be broken except in medical emergencies when the appropriate management of the participant requires knowledge of the treatment randomisation.

The Sponsor retains the right to break the code for SAEs that are unexpected and are suspected to be causally related to an investigational medicinal product and that potentially require expedited reporting to regulatory authorities. Randomisation codes will not be broken for the planned analyses of data until all decisions on the evaluability of the data from each individual participant have been made and documented.

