4.1.4 COVID-19 Symptomatic Participant

Participants who become symptomatic during follow-up will be instructed to call the trial staff who will then advise on how to proceed with clinical testing for COVID-19 if necessary. When participants are suspected of being infected with SARS-CoV-2 based on their symptom (fever or cough or shortness of breath or anosmia/ageusia) and/or positive reverse transcriptase-polymerase chain reaction (RT-PCR) testing, they will be advised to contact hospitals/clinics designated for treatment of COVID-19 per local guidance. Symptomatic participants may be regularly contacted over the phone for safety monitoring until symptom resolution.

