8.3.1 Time Period and Frequency for Collecting AE and SAE Information

AEs will be recorded 28 days after each dose of study intervention.

Solicited AEs will be recorded for 7 days following each dose of study intervention.

SAEs will be recorded from the time of signing of the ICF through the last participant contact.

AESIs will be recorded from Day 1, post-treatment, through the last participant contact.

If the investigator becomes aware of an SAE with a suspected causal relationship to the study intervention that occurs after the end of the clinical study in a participant treated by him or her, the investigator shall, without undue delay, report the SAE to the sponsor.

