8.3.3 Causality Collection

The investigator should assess causal relationship between investigational product and each AE, and answer 'yes' or 'no' to the question 'Do you consider that there is a reasonable possibility that the event may have been caused by the investigational product?'

For SAEs, causal relationship should also be assessed for other medication and study procedures. Note that for SAEs that could be associated with any study procedure the causal relationship is implied as 'yes'.

A guide to the interpretation of the causality question is found in Appendix B to the Clinical Study Protocol.

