9.4 Statistical Analyses

9.4.1 General Considerations

The study has been interrupted to allow a safety review, following the occurrence of a SAE in an Oxford University-sponsored trial in the UK. By that time (07 September 2020), 99 participants had been vaccinated. In order not to delay the local (Japan) vaccine assessment, the analysis strategy has been updated.

The analysis will be done in the following three steps:

- The Primary analysis will include immunogenicity data up to Day 57 from subjects enrolled before the study interruption and safety data gathered in all participants up to Day 57.
- The additional analysis will include immunogenicity data in all participants up to Day 57.
- The final analysis will include all endpoints up to Day 365 in all participants.

The clinical data lock for the primary analysis will occur after all participants have completed visit Day 57 or discontinued early, whichever occurs first. All safety data up to Day 57 in all subjects will be included. This primary analysis will also include immunogenicity data up to Day 57 from subjects enrolled before the study interruption.

After completion of the clinical data lock for the primary analysis, the study will become single blind, where only participants are blinded from allocation of investigational product.

Final clinical data lock will occur when all participants have completed the study or discontinued early.

The statistical analysis plan (SAP) will be finalised prior to the clinical data lock for the primary analysis and it will include a more technical and detailed description of the statistical analyses described in this section. This section is a summary of the planned statistical analyses of the most important endpoints including primary and main secondary endpoints.

All personnel involved in the analyses of the study will remain blinded until the clinical data lock for the primary analysis is achieved and protocol deviations are identified.

The additional analysis including immunogenicity data up to Day 57 in all participants will be performed when these data become available. In addition, the final analysis will be performed when all participants have completed Day 365 visit or discontinued early.

Analyses will be performed by the Sponsor or its representatives.

Categorical variables will be summarised using frequency and percentages, where the denominator for calculation is the underlying analysis set population unless otherwise specified.

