9.4.3.2 Secondary Endpoints

The secondary safety endpoints are the occurrence of SAEs, AESIs (defined in Section 8.3.8) collected from Day 1 through Day 365.

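### Investigators need not be unblinded at the primary-analysis lock; doing so exposes later AESI recognition, causality ratings and COVID-19 case-finding to avoidable assessor bias

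*Protocol*

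**What the plan says.** Before the lock, section 6.3.2 keeps participants, investigators and involved sponsor staff unaware of the "intervention received until completion of clinical data lock for primary analysis". After it: "Only participants will be blinded from their investigational product assignment after clinical data lock for primary analysis". Section 9.4.1 agrees that "the study will become single blind, where only participants are blinded from allocation of investigational product", and the synopsis, the note to the Schedule of Activities and section 4.1.3 say the same. On timing, section 9.4.1 states: "The clinical data lock for the primary analysis will occur after all participants have completed visit Day 57 or discontinued early".

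Data collection continues well past that point:

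- **SAEs and AESIs.** Section 8.3.1: "SAEs will be recorded from the time of signing of the ICF through the last participant contact". AESIs also run to last contact. Section 9.4.3.2: "The secondary safety endpoints are the occurrence of SAEs, AESIs (defined in Section 8.3.8) collected from Day 1 through Day 365".
- **Causality.** Section 8.3.3: "The investigator should assess causal relationship between investigational product and each AE", as a yes/no answer.
- **COVID-19 cases.** Under section 4.1.4 a symptomatic participant calls the trial staff, "who will then advise on how to proceed with clinical testing for COVID-19 if necessary". The Schedule of Activities lists RT-PCR at screening only.

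The protocol names no blinded assessor for the period after the lock and does not limit code release to an analysis team.

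**The concern.** The primary analysis needs treatment codes, but only the people who run and submit it need them. The plan removes the blind from everyone except participants, and so from the people who generate the remaining data.

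Three things they do after the lock involve judgement. First, they recognise AESIs. Some categories in Table 11 are soft: the entry for other neurologic events includes numbness, paraesthesia and weakness. Second, they rate causality. Third, they advise on COVID-19 testing, which feeds the exploratory comparison of RT-PCR-positive symptomatic cases in section 9.4.2.3. Knowing the arm can shift each of these in one arm more than in the other. Staff who know the allocation and stay in contact with participants may also disclose it, which endangers the one blind the plan means to keep.

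There is little to catch such a shift. The Neurological AESI Expert Committee is advisory, covers only selected neurological events, and is not said to be blinded. There is no data monitoring committee.

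**Working it through.** The protocol gives no figure for this point, so there is none to reproduce. The check compares passages and then counts exposed follow-up.

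**Who needs codes at the lock, and who gets them**

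| Purpose | Who needs allocation | What the plan does |
|---|---|---|
| Primary analysis and submission (9.4.1) | Sponsor analysis and submission team | Opens allocation to all except participants |
| Access to a licensed vaccine (4.1.3, 6.3.2) | Participants and sites, when a vaccine is available | Separate, later trigger |
| Medical emergency (6.3.3) | The investigator, for one participant | Individual code break through the IRT |

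None of these purposes requires opening allocation to all sites at the lock.

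**Which endpoints are exposed**

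| Endpoint | Depends on site judgement after the lock? |
|---|---|
| Primary safety to Day 57 | No; data are complete before the lock |
| Spike, RBD and neutralising-antibody results to Day 365 | No; laboratory measurement |
| Nucleocapsid seroresponse | No; scheduled serology at Days 183 and 365 |
| SAE occurrence | Little; seriousness criteria are largely objective |
| AESI occurrence | Yes, for the softer categories |
| Relatedness of SAEs and AESIs | Yes |
| RT-PCR-confirmed symptomatic COVID-19 | Partly, through advice on testing |

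**How much follow-up is exposed**

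Inputs: nominal follow-up from Day 1 to Day 365, i.e. 365 − 1 = 364 days; the lock is no earlier than the last participant's Day 57 (or early discontinuation); 99 participants had been vaccinated by the interruption on 7 September 2020 (9.4.1). The lock date is not given. I assume 18 January 2021 (the date of this protocol version) to 28 February 2021.

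Exposed share = (365 − study day at lock) / 364.

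- Participant at Day 57 on the lock day: (365 − 57)/364 = 308/364 = 85%. This is the upper limit.
- Dosed 7 September 2020, lock 18 January 2021: study day 134; 231/364 = 63%.
- Dosed 7 September 2020, lock 28 February 2021: study day 175; 190/364 = 52%.

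Each further week of delay in the lock removes 7/364, about 2 percentage points. Licensed-vaccine unblinding before Day 365 would shorten the avoidable period further, since allocation is then open to all anyway.

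**The case against.** The single-blind step is deliberate and stated the same way in five places, and no analysis is claimed to be investigator-blinded after the lock. The primary endpoints are protected, and what remains exposed is secondary or exploratory. All of that stands, and it limits the weight of the point. It does not supply a reason for unblinding sites.

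A reader might go further in four ways that the protocol does not support:

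- **That unblinded causality ratings bias the secondary safety endpoint.** That endpoint is occurrence of SAEs and AESIs, and section 8.3.9 requires SAEs to be reported regardless of relatedness. Causality bias touches only relatedness summaries. General AE collection ends at Day 57, so later ratings concern SAEs and AESIs alone.
- **That site staff decide who is tested.** Section 4.1.4 has the participant, who remains blinded until the licensed-vaccine step, start the contact; staff advise, and suspected cases are sent to designated hospitals or clinics. Staff influence ascertainment without controlling it, and nucleocapsid serology does not depend on anyone's choice to test.
- **That the exposed endpoints are most of what the final analysis adds.** It also adds antibody results from Days 183 and 365, which are laboratory measurements.
- **That each participant's assessors are unblinded at that participant's own Day 57.** The lock waits for the last participant, so earlier enrollees are well past Day 57.

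Nor does the protocol give any rates from which to estimate the size of a bias in the case comparison.

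**Conclusion.** The point holds as a cheap improvement. After the primary lock, AESI recognition, SAE and AESI causality ratings and advice on COVID-19 testing rest with people who may know the arm, although only the sponsor's analysis and submission team needs the codes. The exposed results are AESI occurrence, relatedness summaries that run past the lock, and the exploratory comparison of RT-PCR-confirmed cases.

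The exposed share of follow-up is at most 85%. The 52% to 63% for a participant dosed on 7 September 2020 rests on the assumed lock dates. These figures measure exposure to unblinded assessment, not bias; the direction and size of any bias cannot be derived from the protocol.

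Two other statements do not fit the planned unblinding: section 6.3.2 restricts breaking the randomisation code to medical emergencies, and the synopsis disclosure statement describes investigators and sponsor as blinded without any time limit.

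**What to change.** In sections 6.3.2, 4.1.3 and 9.4.1, with matching text in the synopsis and the note to the Schedule of Activities:

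1. State that at the primary lock codes are released only to a designated sponsor analysis and submission team.
2. Keep investigators, site assessors and monitors blinded until the unblinding already planned for licensed-vaccine availability, or until Day 365. Leave that trigger as it is.
3. Reconcile the emergency-only sentence in section 6.3.2 and the unqualified blinding statement in the synopsis with the plan as amended.

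If sites have already been unblinded, report post-lock causality, AESI and COVID-19 case data separately, labelled as collected by unblinded assessors.

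Cost: a protocol amendment with IRB/IEC and regulatory approval, access control on the codes, and sharing results with sites only in aggregate before Day 365. Sites already separate an unblinded pharmacist from blinded staff, so the working practice is not new. No extra participants, visits or samples are needed.

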6.3.3 Procedures for Unblinding

The IRT will be programmed with blind-breaking instructions. In case of an emergency, in which the knowledge of the specific blinded study intervention will affect the immediate management of the participant's condition (eg, antidote available), the investigator has the sole responsibility for determining if unblinding of a participants' intervention assignment is warranted. Participant safety must always be the first consideration in making such a determination. If a participant's intervention assignment is unblinded, the Sponsor must be notified within 24 hours after breaking the blind.

6.4 Study Intervention Compliance

When participants are dosed at the study site, they will receive study intervention directly from the investigator or designee, under medical supervision. The date, and time if applicable, of dose administered will be recorded in the source documents and recorded in the electronic Case Report Form (eCRF). The dose of study intervention and study participant identification will be confirmed at the time of dosing by a member of the study site staff other than the person administering the study intervention.

6.5 Concomitant Therapy

Any medication or vaccine (including over-the-counter or prescription medicines) that the participant is receiving at the time of enrolment or receives during the period specified in the Schedule of Activities (SoA, Section 1.3) must be recorded along with:

- Reason for use
- Dates of administration including start and end dates
- Dosage information including dose and frequency

The Study Physician should be contacted if there are any questions regarding concomitant or prior therapy.

6.5.1 Permitted Concomitant Medications

Participants may take concomitant medications prescribed by their primary care provider for management of medical conditions and/or for health maintenance.

6.5.2 Prohibited Concomitant Medications

- Receipt of any vaccine (licensed or investigational) other than the study intervention (within 30 days before and after each study vaccination).
- Receipt of a product likely to impact on interpretation of the trial data (eg, adenovirus vectored vaccines, any coronavirus vaccines) (within 30 days before study vaccination until the end of study). Note: Participants on the placebo arm are allowed to be vaccinated when a licensed vaccine for COVID-19 becomes available in Japan for the general population.
- Receipt of any investigational drug (from provision of informed consent to the end of study).
- Receipt of any immunosuppressant medication (within 6 months prior to enrolment until the end of study) other than the topical steroids and short courses of steroids (course lasting ≤ 14 days).
- Receipt of immunoglobulins and/or any blood products (from provision of informed consent to the end of study).
- Receipt of oral anticoagulants, such as coumarins and related anticoagulants (ie, warfarin) or novel oral anticoagulants (ie, apixaban, rivaroxaban, dabigatran and edoxaban) (from provision of informed consent to the end of study).

6.6 Dose Modification

Study intervention will be administered as described in Section 6.1.2. Dose modification is not permitted.

6.7 Intervention After the End of the Study

Not applicable.

7 DISCONTINUATION OF STUDY INTERVENTION AND PARTICIPANT DISCONTINUATION/WITHDRAWAL

7.1 Discontinuation of Study Intervention

Each participant will receive 2 doses of study intervention. An individual participant will not receive study intervention if any of the following occur in the participant in question:

- Withdrawal of consent after signing informed consent
- Participant meets one or more of the exclusion criteria or fails to meet all inclusion criteria for study participation
- Participant is pregnant or nursing
- Any Grade ≥ 3 allergic reaction including anaphylaxis that is assessed as related to AZD1222
- Any SAE assessed as related to study intervention
- Any AE that, in the judgment of the site investigator, is related to study intervention and may jeopardise the safety of the study participant

Each participant who has received at least one dose of study intervention will be followed for the full study period, unless consent is withdrawn specifically from further study participation, or the participant is lost to follow-up. Participants who have not received study intervention, regardless of reason, will not be followed.

